4.2.2 SECONDARY ENDPOINTS

KOOS QOL, KOOS-pain, KOOS-Sports/Rec, Biomarker levels in synovial fluid, serum and urine at time of surgery MRI T1rho changes at 2 years

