7 STUDY PROCEDURES AND SCHEDULE

7.1 STUDY PROCEDURES/EVALUATIONS

7.1.1 STUDY RELATED

Demographic information: Demographic data to be collected at Visit 1 will include height, weight, date of birth, age, gender and race.

Medical and Medication History A detailed past medical history and a list of current medication, to include prescription and over-the-counter medications, will be collected at Visit 1. Assessment of eligibility should include a review of permitted and prohibited medications. Both the medical and medication history will be reviewed with the subject throughout the study for any changes in baseline history.

Physical examination including vital signs, height, weight, BMI. All subjects must have a clinical exam that is consistent with an ACL tear at Visit 1. All subjects will have range of motion (ROM) collected at all visits.

Knee Aspiration: All subjects undergo knee aspiration to dryness at initial encounter Visit 1 (1-28 days after ACL injury), Visit 2 (the time of surgery) and again at Visit 3 (4-14 days post-op). Should a subject be enrolled into the study and choose not to undergo ACL reconstruction, subject will receive treatment according to this protocol but, aspiration at time of surgery will be omitted.

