7.3 STUDY SCHEDULE

7.3.1 SCREENING/ENROLLMENT

Visit 1 Screening 1-28 days following injury)

- Obtain informed consent and assent, if necessary, of potential subjects
- Review medical history to determine eligibility based on inclusion/exclusion criteria.
- Review medication history to determine eligibility based on inclusion/exclusion criteria.
- Perform medical examinations and collect vital signs as needed to determine eligibility based on inclusion/exclusion criteria. All subjects must have a clinical exam that is consistent with an ACL tear.
- Collection of urine and blood for laboratory testing. Women of child bearing potential will be given a urine pregnancy test. Test must be negative in order to enroll into the study.
- Subjects will have the following assessments: range of motion, knee instability (Lachman's test) and standardized MTP-2 weight bearing x-rays.
- Standard questionnaires including the KOOS, IKDC, VR-12 and a Likert pain scale.
- Research knee MRI

Following the review of above assessment results and a review of inclusion/eclusion criteria, subjects will be randomized into 1 of 3 treatment groups. Following randomizing, subjects will undergo a knee aspiration and will receive their first dose study medication.

Visit 2 (day of surgery or 4-6 weeks post injury)

- Knee aspiration (in the operating room under anesthesia)
- Patient reported outcomes (PROs) administered prior to surgery
- KOOS, IKDC, VR-12 and a Likert pain scale administered prior to surgery
- Biomarkers (urine and blood) pre-operatively
- Review for AE's and SAE's
- ROM will be performed prior to surgery

Visit 3 (4-14 days After Visit 2)

- Knee aspiration (if clinically indicated)
- Biomarkers (urine and blood)
- Review for AE's and SAE's
- ROM will be performed

Visit 4 (6 month After Visit 2+/- 2 weeks)

- Patient reported outcomes (PROs) administered
- KOOS, IKDC, VR-12 and a Likert pain scale administered
- Review for AE's and SAE's

• ROM will be performed

Visit 5 (12 monthsAfter Visit 2+/- 2 weeks)

- ÀRI
- Patient reported outcomes (PROs) administered
- KOOS, IKDC, VR-12 and a Likert pain scale administered
- Biomarkers (serum and urine only)
- Review for AE's and SAE's
- ROM will be performed

Visit 6 (24 month After Visit 2+/- 2 weeks)

- MRI
- Patient reported outcomes (PROs) administered
- KOOS, IKDC, VR-12 and a Likert pain scale administered
- Biomarkers (serum and urine only)
- Review for ÀE's and SAE's
- ROM will be performed

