7.3.2 SCHEDULE OF EVENTS TABLE

This section should capture the procedures that will be accomplished at each study visit and correspond to the descriptions in the above sections.

Procedures	Screening (Visit 1)	Visit 2 ^e	Visit 3	Visit 4	Visit 5	End of Study Visit 6
Time point	1-28 days post injury	Surgery day or 4-6 weeks post injury	4-14 After Visit 2	6 months After Visit 2 (+/- 2 weeks)	12 After Visit 2 (+/- 2 weeks)	24 months After Visit 2 (+/- 4 weeks)
Informed Consent	Х					
Demographics	Х					
Medical history	Х	Х	Х	Х	Х	Х
Randomization	Х					
Administer Investigational Product	Х					
Concurrent meds	Х	Х	Х	Х	Х	Х
Physical Exam	Х					
Range of motion	Х	Х	Х	Х	Х	Х
Vital signs	Х					
Height	Х					
Weight	Х					
Questionnaires	Х	Х		Х	Х	X
Knee Aspiration	Х	Xa	X ^h			
Biomarkers	Х	Х	Х		X ^d	X ^d
Safety Lab Tests ^b	Х					

Procedures	Screening (Visit 1)	Visit 2 ^e	Visit 3	Visit 4	Visit 5	End of Study Visit 6	
Urine pregnancy tests ^c	Х						
Adverse event evaluation	Х	Х	Х	Х	Х	Х	
X-Ray ^f	Х						
MRI ^g	Х				Х	Х	
a: Should a subject be enrolled into the study and choose not to undergo ACL reconstruction aspiration at time of surgery will be omitted. b: Albumin, alkaline phosphatase, total bilirubin, bicarbonate, BUN, calcium, chloride, creatinine, glucose, LDH, phosphorus, potassium, total protein, SGOT [AST], SGPT [ALT], sodium. c: Urine pregnancy test (women of childbearing potential). d: Serum and urine only e. Should a subject be enrolled into the study and choose not to undergo ACL reconstruction, subject will received treatment according to this protocol. For subjects that do not have ACL reconstruction, the time windows will be relative to Visit 2. For example, Visit 3 will be 4-14 days after Visit 2 f. All subjects must have standardized MTP-2 weight bearing x-ray. Documentation of closed growth plates at screening will be noted in the routine SOC x-ray							

g. All subjects enrolled will have an MRI performed regardless if surgery is to be scheduled or not. However, randomization can be performed prior to MRI as the MRI examination is not necessary or required to diagnose the ACL tear.
h. We will only perform the aspiration at Visit 3 if participants had elected to have surgery performed, and if they have fluid on their

knee.

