The power calculations include several caveats. First, for purposes of power calculation, we did not assume a full repeated measures analysis, but instead analyzed at a single time point (oneyear follow-up). Second, we note that in trials such as this, the power of a non-parametric analysis is never much lower than its parametric analog (the "asymptotic relative efficiency" of the Wilcoxon test is at least 0.95), leading us to conclude that our parametrically based power calculations should apply with equal force to a non-parametric analysis.

Statistical analyses - Results from a sample of this size may not be normally distributed. Therefore, non-parametric statistical measures may be used. Primary outcome measures evaluating for change in KOOS will be assessed at multiple points and will be analyzed for change between groups using Friedman two-way ANOVA for repeated measures. Synovial fluid analyses comparing the three groups at five time points will be analyzed using the Wilcoxon Signed Rank Sum Test with Hochberg corrections for multiple time points. Alternatively, if results are normally distributed or can be transformed (e.g., by log transformation) to meet the criteria for normality for parametric analysis, then repeated measures ANOVA will be utilized comparing treatment groups. P-values of less than or equal to 0.05 will be considered statistically significant.

Predicted Results: IL-1ra, while potent, has had mixed results in the treatment of established OA, possibly due to it's short half-life in vivo. In this trial, we expect that an early intervention with IL-1ra will effectively block the deleterious cascade of joint degradation events after joint injury. We expect a significant effect of IL-1ra on post-injury pain and concomitantly an increase in patient-reported outcomes due to the improved early function

Minimization of bias: Due to the randomized study design and the blinding of the investigator and patient to the drug used, we hope to eliminate any investigator or subject bias. Using broad and previously established enrollment criteria we hope to reduce selection bias to a minimum while protecting potentially vulnerable individuals through the exclusion criteria. Procedural bias and measurement bias will be reduced by the multicenter design and the blinded data analysis.

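### Taken literally, the Hochberg correction for the biomarkers counts the pre-injection Visit 1 comparison, which cannot show a drug effect and can only cost power after dosing

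*Combined protocol and SAP*

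**What the plan says.** The statistical analyses paragraph of section 10.1.1 plans synovial fluid comparisons of three groups, which "at five time points will be analyzed using the Wilcoxon Signed Rank Sum Test with Hochberg corrections for multiple time points". It names no visits and lists no hypotheses. Section 10.1.3, on the secondary endpoints, is marked not applicable, so nothing there narrows the family. The significance rule is "P-values of less than or equal to 0.05 will be considered statistically significant". Non-parametric methods are optional. If the data are normal or can be transformed, repeated measures ANOVA is used instead, and no Hochberg step is stated for that route.

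The schedule in section 7.3.2 marks biomarkers at Visits 1, 2, 3, 5 and 6, and not at Visit 4. For Visits 5 and 6 the footnote reads "d: Serum and urine only". Synovial fluid can therefore come only from Visits 1, 2 and 3. Footnotes a and h omit the Visit 2 aspirate in participants who do not have surgery, and limit the Visit 3 aspirate to operated participants with fluid on the knee.

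On the order of events at Visit 1, section 7.3.1 says: "Following randomizing, subjects will undergo a knee aspiration and will receive their first dose study medication". Section 7.2.1 confirms that the aspirating syringe comes off before the study syringe is attached and injected. The secondary endpoint in section 4.2.2 is "Biomarker levels in synovial fluid, serum and urine at time of surgery".

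**The concern.** Allocation cannot affect a sample drawn before the injection, so any difference between arms at Visit 1 is chance. If that comparison is one of the tests over which Hochberg runs, it uses error allowance without being able to detect a drug effect. The visits that can show one then face a stricter threshold than they need. Among these is the day of surgery, which is the declared biomarker endpoint. With 16 to 20 participants per arm there is little reason to give up power in this way.

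**Working it through.** **1. Which visits can make up the family.** The post-dose biomarker visits are 2, 3, 5 and 6, which is four. Five is reached only by adding Visit 1. In synovial fluid alone the possible visits are 1, 2 and 3: three with Visit 1 and two without. The literal five cannot all be synovial.

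**2. Inputs.** Alpha is 0.05 (section 10.1.1), taken as two-sided because the plan does not say. There are 16 per arm, up to 20 with the attrition allowance, and the biomarker effect size is 1.34 (both section 10.1.1). I read 1.34 as a standardised mean difference. The correlation between visits and the pattern of effect over visits are not given, so they are assumptions.

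**3. The plan's own figure.** Exact two-sample t power uses df = 2n − 2 and noncentrality d√(n/2). For n = 16 and d = 1.34, the noncentrality is 1.34 × √8 = 3.79. Power at 0.05 is 0.956. The stated figure of at least 80% is therefore true as a lower bound for one unadjusted comparison; 10 per arm would already reach 80%.

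**4. Direction.** Hochberg rejects a p-value if some p-value at or above it, say t, satisfies t ≤ 0.05 / (number of p-values ≥ t). A further p-value can only raise that count for the existing values. If the added value itself meets the rule, the next smaller original value met it already. So adding Visit 1 can never help a post-dose test.

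**5. Strictest step, exact t power at d = 1.34.**

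| Tests | Threshold | n = 16 | n = 20 |
|---|---|---|---|
| 2 (synovial, without Visit 1) | 0.05/2 = 0.025 | 0.917 | 0.968 |
| 3 (synovial, with Visit 1) | 0.05/3 = 0.0167 | 0.887 | 0.954 |
| 4 (without Visit 1) | 0.05/4 = 0.0125 | 0.863 | 0.941 |
| 5 (with Visit 1) | 0.05/5 = 0.010 | 0.842 | 0.930 |

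**6. Full Hochberg procedure by simulation.** Each setting had 20,000 trials, 16 per arm, and between-visit correlation 0 or 0.5. The table gives power at Visit 2 with Visit 1 in the family, then without it.

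| Family and effect pattern, d = 1.34 | t test | Rank-sum test |
|---|---|---|
| 3 vs 2, effect at Visits 2 and 3 | 0.92 → 0.95 | 0.89–0.90 → 0.94 |
| 3 vs 2, effect at Visit 2 only | 0.89 → 0.92 | 0.86 → 0.90 |
| 5 vs 4, effect at all post-dose visits | 0.90–0.91 → 0.94–0.95 | 0.87–0.89 → 0.92–0.94 |
| 5 vs 4, effect at Visit 2 only | 0.84–0.85 → 0.86–0.87 | 0.80–0.81 → 0.83 |

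At d = 1.34 the loss runs from 0.022 to 0.047. At an assumed d = 1.0 it runs from 0.034 to 0.104. For example, with the t test and effect at Visits 2 and 3, power is about 0.66 with Visit 1 and 0.755 without.

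**7. Type I error.** The simulated family-wise error over the post-dose visits, with no effect anywhere (t test, correlation 0.5), is 0.034 with Visit 1 and 0.049 without it (three versus two tests). For five versus four tests it is 0.035 and 0.043.

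**8. Fewer aspirates.** Because Visits 2 and 3 do not yield fluid from everyone, assume 12 evaluable aspirates per arm. The noncentrality is 1.34 × √6 = 3.28. Exact t power at the strictest step is 0.749 at 0.0167 and 0.803 at 0.025. With 14 per arm it is 0.830 and 0.871.

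**The case against.** The strongest reply is that the plan never says Visit 1 is tested. The sentence is an unreliable guide to the family: it speaks of three groups in a two-arm trial and of five time points for a fluid sampled at three visits at most. The test it names is paired. In the pilot trial described in section 2.1 (Study 2) that kind of test gave within-arm results, and synovial IL-1α was reported as change from Day 0 to Day 28. Used that way here, Visit 1 is the reference and there is no Visit 1 test to remove. Hochberg is also stated only for the optional non-parametric route.

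All of that stands, and it makes the point conditional. The change-from-Visit 1 reading is not a clean fit either: it gives at most four comparisons (two in synovial fluid), not five, and the sentence says that groups are compared. The text allows both readings, and the same clarification settles both.

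A reader might go further and infer that the plan definitely places Visit 1 in the family, that the biomarker aim falls below its stated power, or that a chance Visit 1 difference will be reported as a treatment effect. The documents support none of these. The family is undefined. Power at the protocol's own effect size and 16 per arm stays at or above 80% in every setting computed. Nothing in the plan says how a Visit 1 difference would be reported.

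**Conclusion.** The point holds as a conditional and minor one. On the literal wording, the family contains a pre-injection comparison whether one counts all five biomarker visits or only the three synovial ones. If Visit 1 is tested and Hochberg is used, the error rate is still controlled, but more strictly than needed, and the post-dose visits lose power. At effect size 1.34 and 16 per arm, the loss at one post-dose visit is about 2 to 5 points. It is about 3 to 10 points at 1.0 SD, an effect size that is my assumption and not the protocol's. It would decide whether 80% is met only if evaluable samples fell to about 12 per arm, also an assumption (75% versus 80% at the strictest step). The five-versus-four figures describe a count that cannot occur in synovial fluid; three versus two is the relevant case for that fluid. If the intended tests are changes from Visit 1, or the ANOVA route is taken, there is no such loss.

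**What to change.** State in section 10.1.1 that between-arm biomarker tests are made only at post-injection visits at which the fluid in question is sampled. For synovial fluid these are Visits 2 and 3; for serum and urine, Visits 2, 3, 5 and 6. Use Visit 1 as the baseline reference or show it descriptively, and leave it out of the Hochberg count.

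The same sentence needs three other corrections, best made together: three groups should be two, the number of synovial time points should match the schedule, and a between-group test should replace the paired one if groups are to be compared.

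The cost is a sentence or two. No information on the drug effect is lost, and power at the post-dose visits can only stay the same or rise.

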- To assume responsibility for the proper conduct of the study and not to deviate from the procedures described in the protocol.
- I am thoroughly familiar with the investigational product(s) as described in the protocol, Investigator's Brochure and any other relevant information sources provided to me.
- I am aware of and will conduct the study in compliance with the protocol, ICH GCP guidelines and all applicable regulatory requirements.
- I agree to permit monitoring and auditing of the study by the Sponsor and its designates, and inspection by appropriate regulatory authority (ies).
- I agree to ensure that all persons assisting with the conduct of the study are properly qualified for their function.

Investigator Name & Signature:

Principal Investigator: [name] Print/Type Name

Signed: _____

Signature

[figure not shown]
Date:

PROTOCOL SUMMARY

Title:	A Prospective, Multicenter, Randomized, Triple-Blinded, Placebo-
	Controlled study of IL-1RA Treatment in Patients with Acute ACL
	Tear and Painful Effusions
Précis: Objectives:	This study aims to establish efficacy and timing of administration, to reduce post-injury pain, decrease inflammatory biomarkers in ACL injured patients undergoing ACL reconstruction and correlate function, patient reported outcomes and MRI findings at 1 years after ACL injury. The study population will include 40 subjects, ages 14-40 who will be randomized into 2 groups (20 subjects per group). 1. Test the efficacy of a treatment protocol using IL-1ra and knee arthrocentesis to alleviate inflammation related knee pain and improve patient-reported outcomes (PRO) following ACL rupture. 2. Determine if intra-articular IL-1ra therapy improves levels of a panel of inflammatory, meniscus and cartilage metabolism, and oxidative stress biomarkers as measured in synovial fluid, serum and urine from patients immediately after ACL injury (baseline, 2 weeks
	after injury and at 1 and 2 years after surgery).3. Answer the question if MRI T1rho changes correlate with synovial biomarker levels and show predictive value for the overall subject patient outcome at 2 years.
Endpoint	Primary endpoint : Change in Patient reported outcomes as measured by KOOS- Symptoms
	Secondary endpoints: KOOS QOL, KOOS-pain, KOOS-Sports/Rec, Biomarker levels in synovial fluid, serum and urine at time of surgery MRI T1rho changes at 2 years
	Study Stopping Criteria

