10 STATISTICAL CONSIDERATIONS

10.1 STATISTICAL AND ANALYTICAL PLANS

10.1.1 GENERAL APPROACH

Sample Size and Power Analysis - The primary outcome aim of the study is to determine if treatment with the study medication results in greater improvements in patient-reported outcomes one year following surgery. We will use the validated Knee Osteoarthritis and injury Outcome Score (KOOS),[27] which is a self-administered, knee-specific instrument that evaluates the course of knee injury and treatment outcomes. To reduce the risk of an underpowered RCT, an a priori sample size estimation was calculated from data collected from recent studies of ACL-injured and -reconstructed patients.[28-32] The previously published oneyear KOOS Quality of Life Scores are 60.2 ± 24.2 [31] and the minimal detectable change of this instrument is 7.2 [32]. Assuming that the standard deviation of the change scores between the day of surgery and one year postoperative visits will be 20% of the standard deviation of the standard deviation of the one-year KOOS Quality of Life Scores ($.2 \times 24.2 = 4.8$), a sample size of 16 patients per group (32total) would be at least 80% powered to detect a difference of 7.2 points between the treatment group and the control group (One-way ANOVA model with alpha = 0.05, Effect size = 7.2/4.8 = 1.5, G*Power 3.0.10). This sample size would adequately power the study for the primary outcome variable, but would also adequately power the study for the second aim of the study. The second aim of the study is to compare chondrodegenerative biomarkers between groups at the 1 year follow up. We have previously observed large effect sizes between groups in preliminary studies (ES = 1.34), and a sample size of 32 patients (16 per group) would be at least 80% powered to detect effect sizes of this magnitude. However, to protect against an underpowered study due to patient attrition, we will monitor compliance and potentially enroll up to 20 patients per group in order to adjust for attrition. Patient costs will not occur until sample or MRI analysis.

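### The primary KOOS analysis is left to be chosen from the outcome data, between methods that answer different questions, with no rule for the choice

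*Combined protocol and SAP*

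**What the plan says.** The Protocol Summary gives the primary endpoint as "Change in Patient reported outcomes as measured by KOOS- Symptoms". Section 4.2.1 names the same subscale without a time point. The only efficacy analysis text is the statistical analyses paragraph of section 10.1.1. Because a sample of this size may not be normal, it says "Therefore, non-parametric statistical measures may be used", and it assigns change in KOOS over several visits to a Friedman two-way ANOVA. After a sentence on synovial fluid it continues "Alternatively, if results are normally distributed or can be transformed (e.g., by log transformation) to meet the criteria for normality for parametric analysis", in which case a repeated measures ANOVA compares the treatment groups. The criterion is "P-values of less than or equal to 0.05 will be considered statistically significant".

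The sample size text in the same section is built on something else: change from the day of surgery to one year, compared between two arms ("One-way ANOVA model with alpha = 0.05, Effect size = 7.2/4.8 = 1.5, G*Power 3.0.10"). Section 10.1.2, headed as the primary efficacy analysis, contains only safety and stopping text. Section 10.1.3 is marked not applicable.

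**The concern.** The plan makes the primary method depend on how the outcome data look, but does not say how to look. It names no normality test or cut-off. It does not say whether scores, changes or residuals are checked, or at which visit. It does not say which ANOVA term is the primary comparison, or that the choice is recorded before unblinding. Two analysts following the text faithfully could report different primary p-values from the same 32 to 40 patients, and in a trial this small one borderline p-value can settle the conclusion. The methods are also not two routes to one answer, so the switch changes the question as well as the test.

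**Working it through.** **1. The plan's own figure.** Inputs from section 10.1.1: difference 7.2, SD of change 0.2 × 24.2 = 4.84 (the plan uses 4.8), 16 per arm, alpha 0.05. Two-sided testing is assumed, because sidedness is not stated. d = 7.2/4.8 = 1.5; noncentrality = d√(n/2) = 1.5 × √8 = 4.24 on 30 degrees of freedom. Power is 98.4%, so the claim of at least 80% is true (9 per arm would do; 8 gives 79.7%). The calculation is for a two-arm comparison of one change score. It matches neither analysis named for KOOS.

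**2. What each method tests.**
- *Standard Friedman:* patients are blocks and visits are ranked within them, so the null hypothesis is no change over time. In simulations with no drug effect and five KOOS visits (the schedule has questionnaires at Visits 1, 2, 4, 5 and 6) it rejected in 100% of trials, because scores change over time. With visits as blocks and arms as treatments it rejected in 21% to 39%, because visits from the same patients are correlated.
- *Repeated measures ANOVA:* either an arm effect averaged over all visits or an arm-by-visit effect. The plan does not say which.
- *Stated aim and power:* the arm difference at one year.

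**3. Inflation when both tests address the same contrast.** Null simulations compared a t-test with a rank-sum test, at 16 and 20 per arm and 20,000 trials per setting, on normal, skewed, heavy-tailed and KOOS-like change data. Five-visit simulations used 10,000 trials per setting and within-patient correlation 0.3 or 0.6.
- Shapiro-Wilk gate at 0.05 applied mechanically: 5.0% to 5.3%.
- Better of the two tests: 5.7% to 6.4% at a single time point. With five visits, 5.8% to 5.9% for the arm effect and 5.5% to 5.9% for change.
- Log version added as a third option: 6.4% to 6.9%.

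The rates stay low because the two tests are strongly correlated (about 0.73 to 0.94 in the single-time-point simulations).

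**4. Inflation across different contrasts.** With equal variances σ² and equal correlation ρ over five visits, the covariance of a change (visit b minus visit a) with the five-visit mean is (1/5)[(σ² + 4ρσ²) − (σ² + 4ρσ²)] = 0. The two tests are then nearly independent, which gives about 1 − 0.95² = 9.75%. Simulated rates for the better of two results:
- rank-sum of one-year change, or the all-visit arm effect: 8.8% to 9.9%;
- arm effect, or arm-by-visit effect: 9.7% to 10.2%;
- arm-by-visit effect, or rank test of change: 8.2% to 8.4%.

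**5. The log transform.** The log of a change is undefined at zero or below. With SD 4.8 and an assumed mean gain m, the affected share is Φ(−m/4.8): Φ(−1.04), about 15%, for m = 5, and Φ(−2.08), about 2%, for m = 10. In simulated KOOS-like data (assumed mean gain about 23, SD 18) it was 10% to 16%. On visit scores the log is workable, since only about 0.1% of simulated scores were zero.

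**6. How often a normality check would switch the method.** This depends on an assumed distribution. For a ceiling-skewed raw score, 100 × Beta(5, 1.5), Shapiro-Wilk rejected in at least one arm in 42% to 44% of trials at 16 per arm. For a Beta matched to the documents' 60.2 ± 24.2 (the Quality of Life subscale) it was about 20%. For change scores it was about 9% to 16%.

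**The case against.** The case for leaving the text alone has four parts.

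- *The rule is a condition, not a licence to report the smaller p-value.* Followed mechanically it holds about 5%. This stands as to size, but the condition cannot be followed mechanically because it is not specified.
- *The trial is blinded.* Section 10.1.1 mentions blinded data analysis, and section 10.2.3 places release of dosing information after data lock. This makes deliberate selection less likely. It does not fix the method, and it does not prevent two coded arms from being compared under both methods.
- *The alternative branch follows the synovial fluid sentence and may concern biomarkers only.* The paragraph opens with results in general and the condition refers to results without restriction, so the natural reading includes KOOS. If it did not, KOOS would be left with Friedman alone, which in its standard form does not compare arms.
- *The rank-sum test used in the simulations is not named for KOOS.* Correct. It stands in for a repaired rank branch, so the rates describe the switch itself and not the defects of Friedman.

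A reader might infer three stronger things. One is that the switch doubles the false-positive rate to about 10%. The documents do not support this: that rate needs the better result to be picked across different contrasts, which the plan leaves open but does not prescribe. Another is that the log transform makes the parametric branch impossible. It does not, because the log is only an example and repeated measures ANOVA can be run on visit scores. The third is that the method is decided by a coin toss. That rests on one assumed raw-score distribution and does not carry over to change scores.

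**Conclusion.** The point holds as a failure of prespecification. The primary KOOS analysis is not fixed, and the methods on offer do not test the same hypothesis or match the one-year comparison that was powered. The mismatch matters more than the alpha inflation, which is small for the switch alone; the larger rate in step 4 of the working is conditional on selection across contrasts. The log difficulty is confined to zero or negative changes, for which the plan has no rule.

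The rates assume two-sided tests, a 0–100 score, and visit means, SDs and correlations that are not in the documents. That no method is fixed, and that a standard Friedman test does not compare arms, depends on none of these assumptions. The change should be made before unblinding.

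**What to change.** For the primary endpoint, delete the alternative branch and state, before unblinding, one between-arm test of KOOS-Symptoms at one year, used whatever the distribution, with its statistic named. One example is the arm difference in mean change from the day of surgery to one year, which is the change used in the sample size text. It could be tested by a t-test or by a re-randomisation test. Re-randomisation must respect the permuted blocks and account for patients replaced under sections 5.4.2, 6.1.9 and 10.2.1. Neither choice needs a normality check or a log transform.

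The starting visit should be written in as well. The day of surgery (Visit 2) comes after the injection at Visit 1, so a change measured from it subtracts any effect already present by then.

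Keep the multi-visit repeated measures analysis, with its term named, as a labelled sensitivity analysis that cannot replace the primary result.

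The cost is a few sentences of SAP text, plus a short program if re-randomisation is chosen, and no extra patients. The sponsor gives up the freedom to switch methods after seeing the data.

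### The repeated measures ANOVA offered for KOOS is not tied to the one-year comparison that the plan sets as its aim and powers

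*Combined protocol and SAP*

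**What the plan says.** The aim in section 10.1.1 is to see whether treatment gives "greater improvements in patient-reported outcomes one year following surgery". The sample size paragraph rests on one comparison at that time, the change score from surgery to one year: "One-way ANOVA model with alpha = 0.05, Effect size = 7.2/4.8 = 1.5". It concludes that 16 per group "would be at least 80% powered to detect a difference of 7.2 points between the treatment group and the control group".

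The next paragraph adds a caveat about the power calculation: "we did not assume a full repeated measures analysis, but instead analyzed at a single time point". The analysis paragraph opens by allowing for non-normal data: "Therefore, non-parametric statistical measures may be used". It assigns KOOS, at several unlisted time points, to a Friedman test. A sentence on synovial fluid follows. The paragraph then says that if results are normal or can be transformed to normality, "then repeated measures ANOVA will be utilized comparing treatment groups".

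Section 4.2.1 names KOOS-Symptoms as primary endpoint without a time point. Section 10.1.2, headed as the primary efficacy analysis, contains only a safety review and stopping criteria. Section 7.3 collects KOOS at Visit 1 (before dosing) and at Visits 2, 4, 5 and 6. Sections 5.4.2, 6.1.9 and 10.2.1 exclude and replace patients who leave before three months. No rule covers a visit missed later.

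**The concern.** The question asked, the comparison powered and the test named are not the same. The question and the power calculation concern one between-arm difference at one year. A repeated measures ANOVA with two arms has a group term and a group-by-visit term, and neither is that difference. The plan does not say which term is primary, so the primary p-value could be chosen after the data are seen. It does not say which visits enter or whether Visit 1 is an outcome or the reference for change. The caveat discloses that power was worked out for a different analysis but does not resolve it.

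At stake are the interpretation of the primary result, the relevance of the stated power to the test used, and possibly the loss of patients who have a one-year score but lack another visit.

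**Working it through.** **1. The plan's own figure.** The inputs are all from 10.1.1: "the minimal detectable change of this instrument is 7.2"; "KOOS Quality of Life Scores are 60.2 ± 24.2"; change SD 0.2 × 24.2 = 4.84, stated as 4.8; 16 per group; alpha 0.05, taken as two-sided. With d = 7.2/4.8 = 1.5, the noncentral t test (the same as a two-group one-way ANOVA) gives 98.4% power, or 98.3% with SD 4.84. The claim of at least 80% is therefore true on these inputs, for the one-year change score.

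**2. What the group term estimates.** Assume that all five KOOS visits enter. Randomisation makes the true Visit 1 difference zero.

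- Effect of 7.2 at all four post-dose visits: (0 + 4 × 7.2)/5 = 5.76, which is 0.8 of 7.2.
- Effect of 7.2 at one year only: 7.2/5 = 1.44, which is 0.2 of 7.2.

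If Visit 1 is left out as an outcome, the same averages over four visits are 7.2 and 7.2/4 = 1.8. The term is then undiluted for a constant effect, but it still does not isolate one year.

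**3. Power of each term on the plan's change SD.** Assume compound symmetry, five visits, 16 per group and between-visit correlation ρ (not given in the plan). Then visit SD = 4.84/√(2(1−ρ)), and the SD of a patient's mean over visits = visit SD × √((1+4ρ)/5).

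| ρ | visit SD | SD of mean | group term, constant effect | group term, one year only | group-by-visit, either pattern |
|---|---|---|---|---|---|
| 0.5 | 4.84 | 3.75 | 98.8% | 18.3% | 99.4% |
| 0.7 | 6.25 | 5.45 | 82.5% | 11.2% | 99.4% |
| 0.9 | 10.82 | 10.38 | 33.0% | 6.7% | 99.4% |

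The interaction has noncentrality (16/2) × 7.2² × 0.8 / (4.84²/2) = 28.3 on 4 and 120 df, whatever ρ is. This depends on Visit 1 being an outcome. With post-dose visits only, a constant effect gives the interaction nothing to detect, and its power is 5%.

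**4. The same comparison with a less extreme SD.** Assume a one-year effect of 1.0 SD, ρ = 0.2 to 0.4, 16 per arm and five visits.

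| Test | Effect at 12 and 24 months | Effect at 12 months only |
|---|---|---|
| One-year ANCOVA on Visit 1 | 80–85% | 80–85% |
| One-year change score | 58–70% | 58–70% |
| Group term | 33–45% | 12–15% |
| Group-by-visit term | 78–90% | 59–73% |

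For an effect constant after dosing, the group term has 86–95% and the interaction 59–73%.

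**5. Complete rows.** Assume 20 enrolled per arm (the plan's ceiling), Visit 1 complete, and an independent miss rate m at each of Visits 2, 4, 5 and 6.

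- m = 5%: 20 × 0.95⁴ = 16.3 complete, against 20 × 0.95 = 19 with a one-year score.
- m = 10%: 20 × 0.90⁴ = 13.1 complete, against 20 × 0.90 = 18.

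**The case against.** A reader might infer that the plan commits to a five-visit ANOVA that dilutes the effect and drops anyone with a missed visit. The documents do not support this.

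- **Visit 1 as an outcome.** This is inferred from the collection schedule. The analysis paragraph speaks of change at several time points, so an early visit could be the reference.
- **Dilution.** This belongs to the group term, which the plan does not name as primary. For a question about change, the interaction is the more natural term. In step 4 it at least matches the one-year change score in each pattern. The group term itself beats the one-year ANCOVA when the effect is constant after dosing.
- **Listwise deletion.** This is a property of the classical method and is not a stated rule. The allowance of up to 20 per group absorbs 5% missed per visit (16.3 against the planned 16), though not 10%.
- **Which branch.** Friedman is named first for KOOS. The ANOVA is the alternative, in a sentence placed after the one on synovial fluid. Its wording is general enough to cover KOOS, but that is a reading.
- **Choosing the test by observed normality.** This adds little by itself. A type I error of 5.0–5.4% was simulated for a rule followed honestly.
- **Disclosure.** The power caveat is open about the mismatch, and powering a simpler comparison is not in itself an error.

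These points make the size of the harm conditional. They do not supply the missing contrast: on any reading, no sentence links the KOOS analysis to the one-year difference.

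**Conclusion.** The concern holds as a failure to specify the analysis. The aim and the power calculation concern a one-year difference between arms. The only KOOS analysis described names no such contrast, term or visit set, and 10.1.2 does not fill the gap. The stated power is correct for the comparison it describes but does not carry over to the repeated measures ANOVA. On the plan's own SD, the ANOVA's power in step 3 runs from 6.7% to 99.4%, depending on the term, the effect pattern and an assumed correlation. The 0.8 and 0.2 factors assume that Visit 1 is entered as an outcome. The 16.3 and 13.1 per arm assume complete-row analysis and the miss rates shown. It cannot be said that the planned test is underpowered or biased toward zero, because the plan does not define it closely enough.

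**What to change.** In 10.1.1 and 10.1.2, make the between-arm difference in KOOS-Symptoms at Visit 5 (one year) the single primary contrast, whatever distribution is observed. Estimate it by ANCOVA, or by a likelihood-based mixed model of the post-dose visits with arm-by-visit terms. In either case use the pre-dose Visit 1 score as covariate and keep all available patients. If the mixed model is chosen, name a simpler covariance structure in advance in case an unstructured one does not converge at this sample size. Add a rank-based ANCOVA as sensitivity analysis.

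Restate the power for that contrast. The stated figure is for change from Visit 2, so it does not describe the Visit 1-adjusted difference either.

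The cost is a small amount of rewording. The schedule already collects the data needed. The restated power may be less favourable than the present statement.
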